## **9.6 ECOG Performance Status**

ECOG Performance Status will be summarized as shift from baseline tables by visit using frequencies and percentages at all scheduled visits where performance status was assessed.

## **10 IDENTIFICATION AND SUMMARY OF PROTOCOL DEVIATIONS**

All protocol deviations will be classified as major or minor. All protocol deviations that can be extracted from numeric or coded study data as well as treatment compliance will be summarized. Protocol deviation classification will be determined and documented prior to data base lock.

### **10.1 Data Quality Assurance**

Accurate and reliable data collection will be ensured by verification and cross check of the CRFs against the investigator's records by the study monitor (source document verification) and by the maintenance of a drug-dispensing log by the investigator. Collected data will be entered into a computer database and subject to electronic and manual quality assurance procedures.

## 12 APPENDICES

### 12.1 Appendix A - Time and Events Schedule

Procedures	Screen	Cycle 1		Cycle 2 to 9	End of therapy	Post Therapy Follow up
		D1	D8 + D15 (+D22 + D29 if retreatment delayed)			
Visit / Cycle Day	Within 4 wks before C1 D1					
1)	2)		3)	4)	5)	6)
Informed consent	X					
Demographics	X					
Medical history	X					
Physical examination	X					
Interval history and symptom-directed exams		X		D1	X	
Clinical assessments: Height (screen only), Weight	X	X		D1	X	
ECOG performance status	X	X		D1	X	X (until PD)
Blood pressure, pulse	X	X	X	D1	X	X (until PD)
Adverse events		Cumulative recording  (whenever observed/applicable)				X 
Concomitant treatments	X	X		D1	X	X 
Clinical laboratory tests						
Hematology, Chemistries, and Urinalysis	X	X	X 	D1 	X	
LH, FSH	X			D1	X	
Pregnancy test (β-HCG)	X 					
Tumor tissue specimens collection	X 					
Pharmacokinetics (sub-study)		X 	D2+D3 			
Cardiac function test LVEF (ECHO or MUGA)	X 2A)			End of C3, C6, C7, C8 	X	X 
ECG (12-lead)	X			D1	X	X 

Procedures	Screen	Cycle 1	Cycle 2 to 9	End of therapy	Post Therapy Follow up
Tumor imaging/evaluation	X 2B)		End of C3 + C6	X	X
Quality of Life questionnaire	X		End of C3 + C6	X	X
Survival follow-up					X
Patient registration	X				
Eligibility criteria review	X	X 			
Randomization 	D-1 to D-4 				
Study treatment		X	D1		

- 1) A window of +/- 3 days will be allowed for scheduled visits/actions, +/- 7 days for 3 monthly follow-ups. If a procedure or visit falls on a public holiday, the patient should be scheduled for the next working day.
- 2) Pre-study evaluations dating back more than 2 weeks prior to treatment start are acceptable.
  - 2A) LVEF: In absence of intercurrent chemotherapy or cardiac medical history, results dating back up to 8 weeks will be acceptable.
  - 2B) Tumor imaging: Assessments of indicator lesions up to 4 weeks prior to treatment start (C1D1) will be considered valid for baseline evaluation.
- 3) Patients who have not recovered sufficiently from treatment-related adverse events within 3 weeks may have their retreatment delayed by up to 2 weeks; patients who cannot be retreated 5 weeks after previous dose, will not receive further study treatment but will still be followed for outcome.
- 4) Start of a new cycle is planned every 3 weeks unless treatment delay is required due to residual toxicity. Per footnote 1, a window of up to 3 days is allowed to schedule tests prior to the anticipated day of retreatment, to assure sufficient recovery from treatment-related adverse events ('toxicity') prior to dosing.
- 5) A full End-of-Therapy assessment will be also required whenever a patient is being withdrawn from the study. The reason(s) for discontinuation will be documented.
- 6) Patients discontinuing study treatment for reasons other than disease progression will be reassessed at 3-month intervals to assess the time to treatment failure (progression / death).
 

Follow-up until progression will be suspended in patients in whom a new cancer treatment has been started without prior documentation of progressive disease.

Information on survival status may be captured by telephone if no follow-up visit is scheduled for other reasons.
- 7) If treatment was discontinued because of a drug-related adverse event (i.e., causality at least possibly related), the patient will be followed up as clinically indicated to assess and document the outcome.
- 8) Only required in women of child-bearing potential
- 9) Only a patient developing signs of cardiac failure during post-treatment follow-up will have LVEF and ECG evaluated; a left ventricular dysfunction of CTCAE grade 4 will be reported as an SAE.
- 10) Only anticancer treatments that a patient received during post treatment follow-up for survival will be recorded.

- 11) For tests performed by a laboratory not affiliated to study site (e.g. mid-cycle controls by the patient's home doctor) copies of the external laboratory reports will be provided to the sponsor and results recorded in the CRF.
- 12) The pharmacokinetic sub-study will be conducted at selected investigational sites. Procedures are described in Appendix 7 of the protocol.
- 13) Every effort should be made to start treatment within 4 days of randomization.
- 14) Specimens from FFPE fresh biopsies if FFPE archival tumor specimens are not available.
- 15) Except for Day 1 clinical laboratory tests
- 16) Recommended to be conducted also at end of Cycle 7 and 8 (i.e., before start of Cycle 8 and Cycle 9, respectively) for both arms. Results are to be captured on the eCRF if there is an abnormal finding.

## **12.2 Appendix B - Progressive Disease and Response Algorithm**

### **12.2.1 Introduction**

This algorithm is designed to determine the following:

- Whether a patient's disease has progressed and, if so, the date of progression
- The censoring date for patients whose disease never progressed

### **12.2.2 Response Evaluation Criteria in Solid Tumors (RECIST 1.1)**

Details can be found in Protocol Section 7.1.

### **12.2.3 Date of Progression or Censoring**

The date of death is the documented date of death. The date of progression (non death) will be determined as follows:

Progression is first observed based on	Date of progression
Unscheduled test prescribed by the investigator based on patients clinical presentation	The date the test is performed

 
Scheduled assessment per protocol
 
	
Assessment done on scheduled visit date + 7 days (Visit Window)	The date of the assessment

 
Assessment done > 7 days after scheduled visit date (Note: this case is not relevant for this trial.)
 
	The date of the next scheduled assessment date after the date of last test indicating no progression. For example, if a patient has an assessment done at Jth scheduled assessment visit with a result no progression and has the next assessment done at (J+4)th scheduled assessment visit (i.e., skipping 4 scheduled assessment visit) with a result showing progression, the date of progression will be the date of (J+1)st scheduled assessment visit.

### 12.3 Appendix C - ECOG Performance Status Criteria

ECOG Performance Status Scale		Karnofsky Performance Scale	
Grade	Descriptions	Percent	Description
0	Normal activity. Fully active, able to carry on all pre-disease performance without restriction.	100	Normal, no complaints, no evidence of disease.
		90	Able to carry on normal activity; minor signs or symptoms of disease.
1	Symptoms, but ambulatory. Restricted in physically strenuous activity, but ambulatory and able to carry out work of a light or sedentary nature (e.g., light housework, office work).	80	Normal activity with effort; some signs or symptoms of disease.
		70	Cares for self, unable to carry on normal activity or to do active work.
2	In bed <50 % of the time. Ambulatory and capable of all self-care, but unable to carry out any work activities. Up and about more than 50 % of waking hours.	60	Requires occasional assistance, but is able to care for most of his/her needs.
		50	Requires considerable assistance and frequent medical care.
3	In bed >50 % of the time. Capable of only limited self-care, confined to bed or chair more than 50 % of waking hours.	40	Disabled, requires special care and assistance.
		30	Severely disabled, hospitalization indicated. Death not imminent.
4	100 % bedridden. Completely disabled. Cannot carry on any self-care. Totally confined to bed or chair.	20	Very sick, hospitalization indicated. Death not imminent.
		10	Moribund, fatal processes progressing rapidly.

5	Dead.	0	Dead.
---	-------	---	-------

## 12.4 Appendix D - Imputation Rules for Missing Dates

**Terminology in this appendix:** first dose = first administration of either AEZS-108 (Arm A) or doxorubicin (Arm B).

The date of event (death/progression) is the documented date of event. The missing date will be handled as follows:

What is missing in event date	Imputed value is
Year	

 
If year is missing or cannot be confirmed to be earlier than the month of last assessment
 
	the year of last assessment

 
If, without considering year, the date of the event is confirmed to be earlier than the date of the last assessment (e.g., January vs. November or May 15 vs. May 1)
 
	the year of last assessment+1
Month	

 
If month of the event is missing or is confirmed to be the same as the year of the last assessment
 
	Month of the last assessment unless the day of death is earlier than the day of the last assessment (5th vs. 10th). In this case the month will be imputed as the month after the month of the last assessment

 
If month of the event is confirmed to be after the year of the last assessment
 
	January
Day	1, unless the resulting imputed date is earlier than the last assessment date. In this case the imputed day is the day of the last assessment

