#### 7.1.1 OS: Definition

OS is defined as the time from randomization to death for any cause during the study. Patients without confirmed vital status are censored on the day they are last known alive. Every reasonable effort will be made to establish vital status of each patient on the last day of the study, that is, the clinical cutoff date established after approximately 384 patients have died. OS will be calculated as follows:

For those who die during the study,

$$\text{overall survival (days)} = \text{date of death} - \text{randomization date} + 1;$$

For those who are alive or vital status cannot be determined at the end of the study,

$$\text{overall survival (days)} = \text{date of censoring} - \text{randomization date} + 1, \text{ with censor indicator indicating a censor.}$$

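### SAP Appendix D: one example for a missing event year contradicts the rule it illustrates, and the month shift does not advance the year after December

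*SAP*

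**What the plan says.** SAP 4.4 sends all partial dates to Appendix D (SAP 12.4). The first table there covers the date of death or progression.

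- **Year row, default.** The year of the last assessment is used "If year is missing or cannot be confirmed to be earlier than the month of last assessment".
- **Year row, exception.** "If, without considering year, the date of the event is confirmed to be earlier than the date of the last assessment", the result is "the year of last assessment+1". The examples given are "e.g., January vs. November or May 15 vs. May 1".
- **Month row.** Its condition is "If month of the event is missing or is confirmed to be the same as the year of the last assessment". The imputed value is the month of the last assessment, "unless the day of death is earlier than the day of the last assessment (5th vs. 10th"), in which case the following month is used. Nothing is said about the year. A second branch gives January when the event year is known to be later.
- **Day row.** A missing day becomes the 1st. If that would put the date before the last assessment, the day of the last assessment is used. This is the table's only check against such dates.

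The dates feed the primary endpoint: "OS is defined as the time from randomization to death for any cause during the study" (SAP 7.1.1). They also feed PFS, a key secondary endpoint (SAP 7.2.4).

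**The concern.** A programmer works from the rule and its examples together. One of the two year examples does not satisfy the condition it is meant to illustrate. The surrounding wording does not settle the matter, because the default Year row compares a year with a month and the Month row compares a month with a year.

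The Month row has a gap of its own. A shift forward from December lands in January, and the table does not say of which year. The Day row's check does not help, since it acts only when the day is missing.

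At stake is the survival time of any patient whose date passes through these rows. It could be lengthened by a year, or end before a visit she attended.

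**Working it through.** The plan gives no figure to reproduce; this is a check of date logic. The rules are those of SAP 12.4. The calendar years are assumed for illustration.

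**1. The two year examples against the rule**

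Rule: imputed year = year of last assessment + 1 if the event's (month, day) is confirmed to be earlier than that of the last assessment; otherwise the year of last assessment.

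| Order of reading | January, November | 15 May, 1 May |
|---|---|---|
| Event first, assessment second | January is earlier: +1, fits | 15 May is later: no shift, contradicts |
| Assessment first, event second | November is later: no shift, contradicts | 1 May is earlier: +1, fits |

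No single order makes both examples fit. The Month row puts the event first (5th against 10th, for a day of death earlier than the assessment day), which identifies the May example as the wrong one.

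Size if the example were followed, with last assessment 1 May 2014, event 15 May and year missing:

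- Rule sentence: 15 May 2014, which is 15 − 1 = 14 days after the assessment.
- Example: 15 May 2015, which is 14 + 365 = 379 days after.
- Difference: 365 days. SAP 7.5 assumes median OS of 9 and 12 months.

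**2. The month shift in December**

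Inputs: last assessment 10 December 2014, event day 5, month and year missing.

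- Year row, default branch: 2014.
- Month row: 5 is earlier than 10, so the month moves from December to January.
- Day row: not used, because the day is known.
- Result as written: 5 January 2014. In 2014, 10 December is day 334 + 10 = 344 and 5 January is day 5, so the date is 344 − 5 = 339 days before the assessment (339 / 30.4375 = 11.1 months).
- With the year advanced: 5 January 2015, which is 21 + 5 = 26 days after.

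For any December assessment on day D and known event day d < D, in a non-leap year, the gap is 334 + D − d days. As D − d runs from 1 to 30, the gap runs from 335 to 364 days (11.0 to 12.0 months).

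Effect on OS, using SAP 7.1.1 (date of death − randomization date + 1) and an assumed randomization on 1 June 2014 (day 152):

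- As written: 5 − 152 + 1 = −146 days.
- With the year advanced: 365 + 5 − 152 + 1 = 219 days.

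**3. Is the defect confined to December?**

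Last assessment 10 November, event day 5: the month becomes December of the same year, and 5 December is 20 + 5 = 25 days after. The rule works. Only a shift from December fails.

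**The case against.** The strongest reply has four parts.

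**The year rule is not wrong.** The operative sentence requires the event to be confirmed as earlier, and it gives 15 May 2014. A reader might infer that applying the rule literally dates events a year late. The text does not support that: the error arises only if the example is allowed to override the sentence. This part stands.

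**The December case is narrow and rests on one reading.** It needs a December assessment, a known earlier day, and month and year both missing. If the year is known to be later, the January branch is correct. If the year is recorded as the same, the record itself conflicts. In ordinary usage the month after December 2014 is January 2015, and applying the Year row again after the month is imputed would also repair the date. The narrowness stands. The repair is not in the plan, however: no order of steps is given, and an imputed month is not a confirmed one.

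**Other provisions limit exposure.** SAP 12.2.3 sets death at its documented date and progression at the test or assessment date, so PFS is barely touched through progression dates. Protocol 10.6.1 requires full source verification of the primary efficacy parameter, and 10.6.2 adds range checks and crosschecks, which would be expected to flag a death dated before an attended visit. This largely stands. Survival status may be collected by telephone at 3-month intervals (Protocol 8.6.2), so incomplete death dates remain possible.

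**A broader rewrite could do harm.** Suppose the year of last assessment were used when the event's month and day are on or after those of the assessment, with a year added otherwise. An event known only as May, after an assessment on 1 May, could not meet the first condition and would gain a year. The present default avoids this. The objection stands and shapes the fix.

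**Conclusion.** The point holds as a wording defect in an operative rule. The May example contradicts the sentence it illustrates under the table's own event-first order, and no order rescues both examples. The Month row, as written, gives a date 11 to 12 months before the last assessment in the December case.

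The possible error per affected patient is large: 365 days if the May example is followed, and 335 to 364 days before the last assessment in the December case. The number affected should be very small. The documents give no count, so that is an assumption, resting on how much of a date must be missing. With about 384 deaths planned for the final analysis, a material effect on the log-rank result is unlikely. A reader might infer that the OS conclusion is at risk; nothing in the documents supports that. The reason to act is that the table sets primary-endpoint dates and costs almost nothing to correct.

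**What to change.** Make four changes to the event-date table in SAP 12.4:

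1. Reverse the second year example, so that the event is on 1 May and the last assessment on 15 May.
2. In the Month row, state that the year increases by one when the shift to the following month passes December.
3. Keep the present default: the year of last assessment, unless the event's month and day are confirmed to be earlier.
4. Require that no final imputed event date precede the last assessment date, whichever part was missing, and substitute the last assessment date if it would.

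The cost is a few lines of SAP text before database lock and a matching check in the derivation program. Design, data collection and clinical procedures are unchanged.

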8.6.2 Follow-up for survival

For patients going off study, survival information will be collected at 3-month intervals, telephone contact is acceptable.

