### **4.4 Missing and Partial Data**

In general, other than for partial dates, missing data will not be imputed and will be treated as missing. The algorithms for imputation of partial dates vary depending upon the parameter and are presented in Section 12.4 (Appendix D - Imputation Rules for Missing Dates.)

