### **7.2.1 ORR and Clinical Benefit: Definitions**

The ORR for each treatment arm will be estimated as the proportion of responders, defined as a patient whose best overall response is PR or better during the treatment period. All responses must be confirmed at least 4 weeks after the initial response is seen. Tumor assessments will occur every 3 cycles ( $\pm 7$  days) during ongoing treatment then, if required beyond the end of treatment, every 3 months ( $\pm 7$  days) while the patient is on study. The last assessment will occur either when progression is confirmed or when approximately 384 randomized patients have died.

Clinical benefit is defined as having stable disease or better lasting for at least 9 weeks.

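### SAP Appendix D limits an imputed death date only by the last assessment, so a partially dated death can fall before a contact at which the patient was known to be alive

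*SAP*

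**What the plan says.** SAP 4.4 makes Appendix D (12.4) the rule for partial dates: "The algorithms for imputation of partial dates vary depending upon the parameter and are presented in Section 12.4". The event part of Appendix D begins "The date of event (death/progression) is the documented date of event" and then gives a single table that serves death and progression alike. Its only reference point is the last assessment:

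- **Month missing, death in the same calendar year:** "Month of the last assessment unless the day of death is earlier than the day of the last assessment (5th vs. 10th"; under the exception, the following month is used.
- **Month missing, later year:** January.
- **Day missing:** "1, unless the resulting imputed date is earlier than the last assessment date". A date that would fall too early is moved up to the last assessment.

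Appendix D does not define the last assessment and does not mention last contact or last date known alive. SAP 4.3 and 7.2.1 use the phrase when describing the tumor assessment schedule. SAP 7.2.1 reads "The last assessment will occur either when progression is confirmed or when"; the second end point there is about 384 deaths, and it is the only one that SAP 4.3 names.

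Two other provisions bear on the point. Protocol 8.6.2 says that for patients off study "survival information will be collected at 3-month intervals, telephone contact is acceptable". SAP 7.1.1 sets the OS censoring date: "Patients without confirmed vital status are censored on the day they are last known alive".

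**The concern.** Tumor assessments and survival contacts run on different clocks. Protocol 8.6.1 ends imaging follow-up at progression and suspends it when a new cancer treatment starts, but survival contacts go on. Alive contacts later than the last tumor assessment are therefore part of the design. Appendix D does not use them when it completes a death date.

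The SAP then treats the same patient in two ways. If she is lost after her last alive contact, her OS time runs to that contact. If her death is later reported with only the year, her OS time may end months before it. Learning of the death shortens the recorded survival to less than what was already observed.

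The death date enters the primary endpoint directly. It determines the order of events in the log-rank test, the Kaplan-Meier medians and the survival proportions at 6 and 12 months (SAP 7.1.2).

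**Working it through.** The documents give no figure for this rule, so there is none to reproduce. The check applies the rule to dates.

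**The rule as a formula.** With the year known, the Appendix D rows for a missing day, or for a missing month and day, reduce to:

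- imputed date = the later of (first day compatible with the recorded parts) and (last assessment)
- conflict = last date known alive − imputed date, when this is positive

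**Bound when only the day is missing.** A conflict needs an alive contact in the month of death. The latest such contact is on day 31 and the earliest imputed day is 1, so the conflict is at most 31 − 1 = 30 days.

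**When month and day are missing.** The conflict is the last alive date minus the last assessment if the death is in the same year as that assessment. If the death is in a later year, it is the last alive date minus 1 January. Neither is limited to a month.

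**Constructed examples** (dates are illustrative; the last assessment is read as the last tumor assessment):

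| Case | Death recorded as | Last tumor assessment | Last known alive | Appendix D date | Days before alive contact | Date with floor at last known alive |
|---|---|---|---|---|---|---|
| A | June 2015 | 10 Mar 2015 | 20 Jun 2015 | 1 Jun 2015 | 19 | 20 Jun 2015 |
| B | 2015 | 10 Mar 2015 | 15 Sep 2015 | 10 Mar 2015 | 189 | 15 Sep 2015 |
| C | 2016 | 10 Nov 2015 | 20 May 2016 | 1 Jan 2016 | 140 | 20 May 2016 |
| D | July 2015 | 10 Mar 2015 | 20 Jun 2015 | 1 Jul 2015 | none (11 days after) | 1 Jul 2015 |

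Arithmetic for B: 21 + 30 + 31 + 30 + 31 + 31 + 15 = 189 days. For C: 30 + 29 + 31 + 30 + 20 = 140 days. Case D shows that the rule does no harm when the last alive contact falls in an earlier month than the death.

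**How often, under assumptions.** The documents give neither the time from last tumor assessment to death nor the number of partial dates. The following simulation therefore rests on assumed inputs: alive contacts every 91 days after the last tumor assessment, and exponential time from that assessment to death with a median of 4, 6 or 9 months. Ranges are over the three medians.

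| Missing parts | Deaths dated before an alive contact | Mean backdating from true death, as written | Mean backdating, floor at last known alive |
|---|---|---|---|
| Day only | 11% to 13% | about 14 days | about 13 days |
| Month and day | 53% to 69% | 102 to 137 days | 39 to 41 days |

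The percentages are of deaths with that kind of partial date, not of all deaths. With the floor at the last date known alive, no imputed death precedes an alive contact.

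**The case against.** The strongest answer is that the last assessment is undefined, and that for a death it could include a survival follow-up, which is a scheduled procedure in the flow chart. On that reading the conflict largely disappears. Nor is the SAP's usage uniform: section 7.2.1 ends assessments at progression, while section 4.3 mentions only the cutoff at about 384 deaths. This stands in part: a wrong anchor is not proven. But both sections use the phrase for tumor assessments, Appendix D applies one table to death and progression, and no other provision stops a death from being dated before an alive contact. A programmer could reasonably follow the tumor reading.

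It can also be said that partial death dates should be few. Protocol 10.6.1 requires source verification of the primary efficacy parameter in every patient, and SAP 7.1.1 requires every reasonable effort to establish vital status at the cutoff. That stands, and it limits the size. So does the small effect of the floor when only the day is missing.

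Three stronger readings are tempting but not supported:

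- **Bias from regional missingness.** A reader might infer that missing dates concentrated in one region would bias the comparison. Patients are randomized centrally 1:1 (Protocol 8.3), so in expectation such missingness falls on both arms alike. Bias needs missingness that differs by arm, and the documents give no reason to expect it.
- **A typical error of months.** Under uniform dates within a calendar year, the gap from last assessment to true death averages 3.0 months, with a 95th percentile of 8.4 months. That does not measure how often, or by how much, an alive contact is contradicted, and it applies only when the month is missing.
- **A need for midpoint imputation.** The earliest permitted date is a legitimate convention. The conflict comes from the floor, not from that choice.

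**Conclusion.** The point holds as a correctable gap in the rule for the primary endpoint's event date. If the last assessment is read as the SAP uses it elsewhere, an imputed death can precede a contact at which the patient was alive. The conflict is at most 30 days when only the day is missing. It can be several months when month and day are missing; the 189 days of case B are about 6 months, against planned medians of 9 and 12 months.

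The effect on the hazard ratio cannot be computed, because the number of partial death dates is not given. It is probably small. The number of events and the planned power do not change, since the rule alters when a death is counted and not whether it is counted. No direction of bias between arms is shown. The case for changing the rule is that it allows impossible dates in the primary endpoint and that the remedy is nearly free.

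**What to change.** Split the event table in Appendix D.

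- **Death:** take the earliest date compatible with the recorded parts that is not before the later of the last assessment and the last date known alive from any source (visit, telephone, laboratory, treatment). The same day must be allowed, because a patient can die on the day of her last contact.
- **Progression:** keep the present rule, and state that the last assessment there means the last tumor assessment.
- **Optional sensitivity analysis of OS:** use the latest date compatible with the recorded parts, capped at the date of the death report or the data cutoff.

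The cost is a few lines in the SAP before database lock and a small programming change. It needs no new data collection, because SAP 7.1.1 already requires a last-known-alive date for OS censoring and the other contact dates are recorded in the study.
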